Self-Report Healthcare Service Use. We will use the Treatment Services Review (TSR) to measure health services use, which has adequate reliability and validity.⁷⁰ We will also access VHA electronic health data, focusing on primary care; substance abuse treatment, and psychiatric treatment services (including mutual aid groups such as AA, receiving detox services, and other substance abuse care settings).

Health Care Utilization using Medical Records. In the last year of the study, a review of participants' medical records will be conducted to determine diagnoses, service use (i.e., ED visits, hospitalizations, primary and specialty care) for one year pre- and post-entry into the study. We will use these data to assess agreement with self-report service use, particularly VHA services, and seek to understand sources of discrepancy. Data will be accessed through CPRS, Corporate Data Warehouse (CDW), and the Joint Legacy Viewer (JLV).

Health Functioning. One item from the SF-12⁷¹ will assess perceived health functioning, which are accepted

Table 2: Study Measures	Instrument	When*	#Min
Primary Outcomes			
Alcohol Consumption	TLFB	B, 3,6,12	20
Secondary Outcomes			
Alcohol Consumption	AUDIT	S, 3, 6, 12	5
Alcohol Consequences	SIP	B, 3, 6, 12	5
Health Service Use	TSR/CPRS	B, 3,6, 12	10-15
Health Functioning	SF-12	S, 3,6,12	
Depressive Symptoms	PHQ-9	B, 3,6,12	
PTSD Symptoms	PC-PTSD-5	B, 3,6,12	
Substance Use	ASSIST	B, 3, 6, 12	
Opioid Misuse	COMM	B, 3, 6, 12	
Problem Severity	BAM	B, 3,6,12	
Individual Factors			
Demographics	SAOM	S/B	5-10
Motivation to Change/Readiness	Rulers	B, 3, 6, 12	
Self-Efficacy	Ruler	B, 3, 6, 12	
Social Factors			
Social Support	mMOS	B, 3, 6, 12	10
Peers Services	WAI-SR	3	
Intervention Interaction	Metric, Sentiment		0

*S=Screen; B=Baseline, 3-month, 6-month, 12-month follow-ups

Veterans.²⁹

Substance Use

Alcohol, Smoking, and Substance Involvement Screening Test (ASSIST) is a structured interview for alcohol, tobacco, cannabis, stimulants, sedatives and opioid use disorders in general medical settings. We will use a brief screening for tobacco use (ASSIST-LITE) and the full ASSIST version 3 to measure use of all other substances.

Opioid Misuse: a modified version of the Current Opioid Misuse Measure (COMM) will assess extent of opioid medication misuse.

Individual Factors

Demographics: Background characteristics assessed include: age, sex, marital status, education, employment, income, legal history, deployment history, etc.⁷⁷

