Data Management. The project's data manager will conduct all data management and analysis activities under the supervision of Drs. [name] and [name]. Research staff will use double entry procedures and reconcile discrepancies. Data cleaning will be conducted throughout data collection to ensure a quality final dataset for analysis. Statistical Analysis System (SAS) will be used to examine and prepare data for the analysis.

General analytic approach. Hypotheses will be planned a priori, and will be limited to the examination of a limited number of outcomes. We will utilize an "intent-to-treat" approach. All analyses will use two-sided tests because it is possible that the APM participants might have worse outcomes compared to CBA participants. Analyses will begin with descriptive data analyses to determine distributions of key variables, to collapse categories, if necessary, and to review data for outliers and clear anomalies. Tests for linearity, independence, missingness, and distributional assumptions will also be performed. Normalizing transformations of the dependent variables will be utilized, if necessary. We will validate the randomization scheme by comparing the initial groups on key variables that could be associated with the outcomes. Where we identify significant differences between groups, we will adjust for these variables, as well as other addictions treatment received if it was not initiated by referral from the APM or CBA clinician (and thus a potential mediator of effect). Prior to fitting any analytic models, a graphical exploration of the outcome variables will be conducted to select the appropriate models based on variable distributions.

Missing data. Every effort will be made to minimize missing data. Where we have missing covariates that are necessary for analysis, we will perform multiple imputation of missing data and combine the results from 5 imputations based on Rubin's method to produce an estimate and the corresponding confidence interval accounting for missing data uncertainty.⁸⁸ For follow-up attrition, the proposed mixed-effects regression model will allow the use of data from all participants (not just those with complete follow-up) and provide unbiased

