Data Analysis for Aim 2: The focus of Aim 2 is to study intervention effects on secondary outcome of frequency of primary care and mental health specialty care visits (as two separate outcomes) from the TSR, calculated as an average number of visits per month during each follow-up period. Similar to Aim 1, analyses will generally use a mixed effect model framework. As described above, initial analyses will examine the distribution of outcome measures over follow-up in order to select an appropriate model (e.g. Poisson regression or a related method for counts of visits). Our analysis strategy will parallel Aim 1 in terms of the independent variables, *random effect for peer/brief advice, focus on time-average treatment effects, and additional modeling of interactions of group and time.*

Secondary Aim will determine the mediators (e.g., motivation to change, self-efficacy, coping, social support) of the effect of the intervention and linkage on subsequent alcohol use and alcohol-related consequences. **Hypothesis:** The effect of randomization to APM compared to BA on the primary outcomes (i.e., alcohol consumption and consequences) will be mediated by differences between groups in motivation to change, self-efficacy, and perceived helpfulness of peer support.

Data Analysis for Secondary Aim: *In order to establish temporal ordering, we will examine whether level of the hypothesized mediators at 3 and 6 months post-baseline mediates the effect of random assignment on 6- and 12-month measures of the three primary outcomes of alcohol use behaviors.^{90,91} We will first determine the whether study condition is associated with the hypothesized mediators over the first six months of follow-up and check for a direct effect of the mediators at 3 and 6 months on alcohol use as measured at 6- and 12-months follow-up. We will estimate the indirect effect of the intervention on alcohol use through the mediators and conduct significance testing of this effect using macros created by Preacher and Hayes.⁹²*

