Data Analysis for Exploratory Aim: Interviews will be audiotaped and transcribed verbatim for content. We will conduct analyses. We will use a rapid data analysis process, a technique used when there is a need for targeted, actionable information.⁹³ The research team will read early transcripts independently, and, in an iterative process, meet to develop and refine the coding scheme and code definitions, including developing new codes from the data based on ongoing data analysis. We will document code definitions, data interpretation, and analytic decisions in memos. Once the research team has agreed on codes and code definitions, Drs. [name] and [name], and the research supervisor, will independently review and code transcripts, meeting regularly to compare coding results, and resolving discrepancies through a consensus process. If coding definitions are refined during this process, the coders will recode transcripts already coded. Once data are coded, we will use QSR NVivo 10 software to organize the data. The study team will meet regularly to discuss code summaries and memos, developing findings with a focus on barriers and facilitators to implementation and potential testable implementation strategies. Members of the study team have used similar methods in a study of the acceptability of peer support interventions in Michigan NG soldiers.^{94,95}

Power and Sample Size Calculations

Of 450 participants randomized, we expect that at least 80% of participants will be retained (n=360). We conservatively have estimated power without accounting for methods that will allow inclusion of participants with partial follow-up data because this benefit will be off-set to an unknown degree by the additional parameters estimated in a mixed effects model. All power analyses used G*Power 3.1.9 software and a two-sided $\alpha = .05$. We calculated power based on several potential outcome measure distributions. If a linear model is appropriate, which we expect to be the case for the primary outcome of total AUDIT scores, we achieve 80% power to detect an effect size (Cohen's d) of 0.30. This is a relatively modest and reasonable effect size for studies of SBIRT models of alcohol brief interventions. For an outcome with a count distribution and assuming a mean level in controls of 1 (e.g., an average of 1 alcohol-related treatment visit in a follow-up period), we achieve 80% power to detect an incidence rate ratio of 0.75 or 1.34 under a Poisson framework.

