We expect that 15% of the screened patients will have a positive screen and will be randomized, yielding 225 per group (total=450). Based on data from the study site, we anticipate the gender composition of the sample to be approximately 7.5% female and 92.5% male; we expect the following racial composition of the sample: approximately 20% African American, 75% Caucasian, and 5% other (i.e., Asian, American Indian, Native Hawaiian or Other Pacific Islander). We also expect that 1-2% of adults will identify as Hispanic ethnicity.

Inclusion criteria for screening. 1) adult Veterans age 18 years of age or older presenting for care in the VAAAHS ED; 2) medically stable and able to provide informed consent.

Inclusion criteria for the RCT. Individuals will be eligible to participate in the RCT if they: (1) have an AUDIT-C score of 4 or more for men and 3 or more for women in the prior 3 months, indicating that they meet criteria for hazardous use (NIAAA 2005; World Health Organization); 2) a telephone and/or the ability to provide information about individuals who can help contact the participant. Importantly, the study will include those with more severe problems to address the problems and needs of Veterans who can most benefit from linkage to primary and secondary care. The more severe users will receive content that actively encourages treatment initiation.

Exclusion criteria for screening. (1) patients who do not understand English; (2) prisoners; (3) current or recent substance use treatment in past 3 months; (4) patients currently in or having received peer services in the past 3-months per medical record; (5) pregnant women; (6) patients deemed unable to provide informed consent as stated above; and (7) profound psychotic symptoms and/or cognitive deficits that would prevent patients from understanding the content of the intervention and/or assessments.

It has been our experience that some patients are unable to provide informed consent on entry to the ED (e.g. psychotic symptoms; acute intoxication) but that their status will improve sufficiently prior to ED discharge to make them eligible to be approached by research staff. Participants may be excluded at the discretion of the Principal Investigator based on participant or study staff best interest (e.g., if participant should become physically or verbally aggressive towards study staff, or if the study staff know a patient or their family

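### The mediation analysis states no baseline covariates and does not fix which mediator visit goes with which drinking visit, so baseline severity could create or mask mediation

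*Combined protocol and SAP*

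**What the plan says.** All references are to the combined protocol and SAP.

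- **Data Analysis for Secondary Aim.** With temporal ordering as its declared purpose, the plan states: "we will examine whether level of the hypothesized mediators at 3 and 6 months post-baseline mediates the effect" of assignment on 6- and 12-month drinking. It will then "check for a direct effect of the mediators at 3 and 6 months on alcohol use as measured at 6- and 12-months follow-up". The indirect effect is tested with published macros; the title of the cited paper (reference 92) refers to simple mediation models. No covariate is named and no visit pair is excluded.
- **Data Analysis for Aim 1.** The TLFB model includes the baseline value of the outcome. Aim 2 and the moderator analyses are explicitly tied to that framework. The mediation paragraph is not.
- **General analytic approach.** Adjustment is planned for variables that differ significantly between arms, and for other addiction treatment that did not come from study referral.
- **Table 2 and Measures.** The "Motivation to Change/Readiness" rulers, the self-efficacy ruler and the mMOS social support scale are collected at baseline, 3, 6 and 12 months, as is TLFB. The TLFB covers 30 days. The WAI-SR, the only peer-service measure, is taken at 3 months only. Coping is listed as a candidate mediator, but Table 2 shows no instrument for it.

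**The concern.** Randomisation protects the path from arm to mediator. It does not protect the path from mediator to drinking, because nobody is assigned to a level of motivation or self-efficacy. A participant's baseline severity may influence both the 3-month mediator and the 6-month TLFB. A regression of drinking on mediator and arm alone then picks up that shared cause, and the product of the two paths inherits the bias. A rule that adjusts only for arm imbalance does not help, since a perfectly balanced covariate can still confound mediator and outcome.

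Timing adds a second problem. If 6-month mediators are paired with 6-month TLFB, the drinking window closes before the mediator is rated, which is the reverse of the ordering the plan wants.

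At stake is the trial's statement about how APM works. APM is designed to move these mediators, and that is the condition under which the false-positive rate rises.

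**Working it through.** **1. The plan's own figure.** The power section assumes "we expect that at least 80% of participants will be retained (n=360"), so 180 per arm, with two-sided alpha .05, and says "we achieve 80% power to detect an effect size" of d = 0.30. Check: z = 0.30 × √(180/2) = 2.846; power = Φ(2.846 − 1.96) = 0.81. It reproduces. The plan gives no power or error rate for mediation.

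**2. Source of the bias.** Assume unit variances and no mediator effect. Baseline drinking loads λ_M on the follow-up mediator and λ_Y on later drinking; APM shifts the mediator by *a* SD. Without baseline drinking in the model:

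- the apparent mediator coefficient tends to b = λ_M × λ_Y;
- the apparent indirect effect tends to a × λ_M × λ_Y.

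With baseline drinking in both regressions, b tends to 0.

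**3. Size.** By hand, the false-mediation rate is roughly P(arm path significant) × P(b significant), with z_a = a√360/2 and z_b = b√360/√(1 − b²). At a = 0.3 the first factor is the 0.81 from step 1. The simulations used n = 360 and a Monte Carlo 95% interval for the product of paths; runs differ by a few points. All loadings and shifts are assumptions.

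| λ_M / λ_Y | a (SD) | b | Hand approximation | Simulated, unadjusted |
|---|---|---|---|---|
| 0.3 / 0.3 | 0.3 | 0.09 | 0.81 × 0.40 = 33% | 29% to 33% |
| 0.3 / 0.5 | 0.3 | 0.15 | 0.81 × 0.82 = 67% | 59% to 66% |
| 0.5 / 0.5 | 0.3 | 0.25 | 0.81 × 1.00 = 81% | 82% to 84% |
| 0.1 / 0.5 | 0.3 | 0.05 | 0.81 × 0.16 = 13% | about 8% to 11% |
| 0.3 / 0.5 | 0.1 | 0.15 | 0.16 × 0.82 = 13% | about 8% to 11% |
| 0.3 / 0.5 | 0 | 0.15 | 0.05 × 0.82 = 4% | about 4% |

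Adjusted for baseline drinking, the first three rows fall to 3% to 6%.

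The sign matters. With both loadings positive and an upward shift, every spurious result at 0.3/0.5 pointed towards more drinking. With λ_M = −0.3, 62% of trials showed a spurious beneficial mechanism.

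**4. A second data model.** Baseline mediator and baseline drinking correlate at ρ, and each tracks over time with stability 0.6. Then b = 0.6 × 0.6 × ρ = 0.36ρ and the apparent indirect effect is 0.36aρ. For a = 0.3 this predicts −0.0216, −0.0324 and −0.0540 at ρ = −0.2, −0.3 and −0.5; the simulated means were −0.0218, −0.0319 and −0.0537 (2,000 trials each).

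| a (SD) | False mediation, unadjusted (ρ = −0.2, −0.3, −0.5) | With baseline mediator and TLFB |
|---|---|---|
| 0.3 | 22%, 41%, 77% | 5.0%, 5.0%, 4.3% |
| 0.5 | 27%, 54%, 93% | about 5% |
| 0 | 1%, 2%, 4% | under 1% |

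**5. Reverse causation.** Now let APM lower drinking by 0.3 SD and let drinking drive the mediator at the same visit (coefficient −0.3, then −0.5), again with no mediator effect.

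| Mediator → drinking visit | Unadjusted | + baseline mediator and TLFB | + TLFB at mediator visit |
|---|---|---|---|
| 6 → 6 months | 16%, 34% | 21%, 44% | impossible: it is the outcome |
| 3 → 6 months | 14%, 34% | 16%, 48% | 0.2%, 0.3% |
| 6 → 12 months | not run | 20%, 44% | not run |

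Baseline adjustment does not cure this, and nor does lagging alone. Adjusting for drinking at the mediator's own visit does, and only lagged pairs permit that.

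**The case against.** The strongest reply is that the plan is silent, and silence is not a decision. A reader might infer that the authors chose an unadjusted analysis. The text neither states nor excludes covariates. Mediation is applied to the same drinking outcomes as Aim 1, and if Aim 1's baseline covariate carried over, most of the modelled confounding would go: adding only baseline drinking to the outcome regression cut 63% to 3% at loadings 0.3/0.5. This stands as a limit on the wording. It does not remove the point, because the neighbouring analyses carry the Aim 1 framework over explicitly and this one does not, and Aim 1 has no baseline mediator to carry over.

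A reader might also infer that a same-visit analysis at 6 months is planned. The documents do not support that. Listing 3 and 6 months against 6 and 12 months, under a stated purpose of temporal ordering, may well mean 3 to 6 and 6 to 12. The text simply does not say so.

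A third tempting reading is that any mediator APM moves, if correlated with baseline drinking, will appear to be a mechanism. That is too strong. The rate is about 8% to 11% when a loading or the shift is 0.1, and the bias can run against the hypothesis and hide real mediation. The documents give no loadings, shifts or signs.

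Finally, adjustment for the baseline mediator is not possible for everything named. The WAI-SR has no baseline value and coping has no listed instrument. This stands and shapes the fix.

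**Conclusion.** The point holds as an under-specification of a secondary aim. Followed literally, the mediation paragraph leaves the mediator-to-drinking path open to confounding by baseline severity, and leaves the visit pairs open to a reading that conflicts with its own purpose.

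With no true mediator effect, unadjusted false mediation ran from about 8% to 11% under weak assumptions to about 30% to 84% with loadings of 0.3 to 0.5 and a 0.3 SD shift. The second data model gave 22% to 93% for shifts of 0.3 to 0.5 SD. With baseline adjustment the rate is around 5% in both models. There is no inflation if APM does not move the mediator. The mechanism is general; the rates depend on inputs the documents do not supply.

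The primary efficacy comparison does not use these models, so nothing here bears on it. The change should be made, but the trial's main conclusion does not depend on it.

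**What to change.** Amend the Secondary Aim analysis text to state that:

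1. Both mediation regressions adjust for baseline TLFB, sex and AUD stratum, and for the baseline value of the mediator where it is collected (readiness, self-efficacy, mMOS).
2. The WAI-SR has no baseline value, so its results carry weaker support. Coping needs a named instrument or should be dropped from the mediator list.
3. Permitted pairs are the 3-month mediator with 6- or 12-month drinking, and the 6-month mediator with 12-month drinking.
4. A sensitivity model also adjusts for TLFB at the mediator's own visit.
5. Reports will say that unmeasured post-baseline confounding may remain.

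The cost is a few covariates already collected, slightly more analysis work and a short wording change. No new data are needed unless coping is kept.

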Finally, because many hazardous/harmful drinkers require linkage to services, in prior work in the ED among adults with substance use disorders, warm referral to a multi-session, in-person case management intervention increased treatment assessment ($OR=1.79$, $p<.001$) and engagement ($OR = 1.48$ $p<.05$)⁴² however, only 50% attendance with the therapist-delivered case management underscores barriers to referrals that could be more directly addressed by peers who have credibility as well as training in service options, leading us toward the peer approach proposed in this application. **Thus, our team has prior experience screening for alcohol in the ED, and delivery of interventions, with exceptional retention with longitudinal follow-up.**

Peer Support Interventions. Peer outreach programs have had wide acceptance in the VHA and numerous "grass roots" peer programs have been implemented within the VHA, and more generally in the military and National Guard (NG).⁵³ One of the leading peer outreach and linkage to mental health or other community resources in the NG is the Buddy-to-Buddy (B2B) Volunteer Veteran program implemented in the Michigan NG. Co-I Dr. **[name]** and others conducted a qualitative study of the role of peer support and linkage to treatment among Michigan NG soldiers which informed the development of the B2B program. In this program, Volunteer Veterans from the community who are outside the NG chain of command are trained in communication skills, attend drill weekends, are available by telephone to offer support and linkage to a variety of community, VA, and NG/military resources. Papers describing the partnership and development of B2B have

been published.⁵⁴ Peer support efforts, such as B2B, provide key potential resources to increase the impact of Screening, Brief Intervention and Referral to Treatment (SBIRT) but have not been used for alcohol misuse.

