Alcohol Brief Advice Content. Participants who are randomized to either condition (APM or BA) will receive a modified BI (brief personalized advice guided by a script, a short pamphlet on alcohol, other health issues, and VHA contact information, and an infographic sheet about VA drinking guidelines as an additional layer of advice). In the APM condition, the brief advice session will be followed by 6 sessions of peer mentoring over 2 months. The BA condition includes the initial brief personalized advice and pamphlet. Materials for the APM and BA sessions will be provided in the ED. Participants may have the option to complete the session in-person or on the phone up to two-weeks after enrollment. The proposed brief advice for both the APM and BA groups will be short and personalized, based on factors such as gender, and severity of hazardous/harmful drinking.⁵⁰ The alcohol brief advice pamphlet to be given to the participants will provide information on alcohol and resources available at the VHA and in the community, with places for the peer to add tailored content (e.g. alcohol issue; reasons for use, strengths to help with change; plans for change, etc.) to: 1) enhance the Veteran's cognitive preconditions for message processing or acceptance (receptivity); and 2) enhance message impact (salience) by selectively modifying behavioral determinants of desired outcomes. Tailoring allows broad topics to be narrowed to participant experience for relevance in a short time period. The APM intervention includes the peer establishing an ongoing relationship with the patient to share their story, and schedule a time for the first Post-ED 'booster'.

6-session Peer Mentorship. Peer mentors will provide structured booster support to Veterans who have been assigned to the intervention condition. The peer mentor will work with each participant in the APM condition over a 2-month period to discuss strategies for reducing hazardous drinking, support behavior change and encourage linkage to care. Peer mentors will address participants' goals and will provide emotional, informational, and appraisal support designed to help Veteran engage in primary and specialty care, as needed. Cases will be reviewed on a weekly basis by the project supervisor and one of the clinical investigators ([name] and [name]). Training will be manualized, peers will receive weekly supervision, and post-ED sessions will be audiotaped.

Table 1: Overview of Peer Mentor Post-ED Visits

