6: Plannin g for the Future	
 Solicit Veteran's issues and questions since last contact Encourage decreased alcohol use with strategies Review coping, social support and leisure options Review solutions to barriers and service options Encourage contact with primary and/or specialty care Summarize progress and plans

current usual practices of ED-based brief interventions and current staffing models. One-session brief clinician advice by a social worker in the ED has had mixed and modest positive effects, but it remains the cornerstone of most alcohol brief interventions in large health systems. Thus, the comparator will be real-world relevant, potentially helpful yet also conservative in terms of the extent to which it can influence longer-term drinking outcomes.

Peer Mentor Hiring, Training, and Supervision. Peer mentors will be hired according to current policy guidelines provided by the VHA Office of Peer Support Services. As is standard practice in VHA programs, we will not require the peer specialist to be matched with study patients on specific demographic characteristics (e.g. military service era, gender) because these requirements introduce practical and ethical hiring challenges and are unlikely to be upheld if the program is implemented across VA facilities with existing peer specialists. However, preference will be given to peer specialist applicants with experience with hazardous drinking/substance use disorders.⁵⁷ Peer specialists will complete standardized VA peer support training and certification through a training program approved by the Office of Peer Support Services. An example training

Peer Mentor Content. Peer mentors will deliver the brief advice in the ED and will initiate conversations with the patient for up to 6-sessions over 2 months post-ED visit. Strengths-based discussions will include a combination of scripted and open-ended content to best facilitate reductions in drinking and engagement across severity (see Table 1). All sessions will be audiotaped and will emphasize strengths and goals, focusing on reducing/stopping alcohol use and linkage to care and barriers (e.g., transportation, going with the Veteran to the first appointment, housing, job or family issues, etc.).

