Brief Advice Condition. Participants assigned to BA will receive brief alcohol advice from a research assistant. Content is comparable in intensity and scope to the current computer protocol that is required to be used in VHA primary care, and a health pamphlet with VHA and community resources and information about alcohol use and other issues. Those randomized to the BA condition will receive no post-ED sessions, consistent with

program offered by the National Alliance on Mental Illness (NAMI) consists of 10 two-hour sessions including topics such as stigma, self-disclosure, disorder-specific information, suicide prevention, and recovery.⁵⁸ Online training is also available through the New England MIRECC Peer Education Center. Peer mentors will be trained by experienced investigator trainers ([name], [name], [name]) in alcohol issues, intervention content, linkage in primary and specialty care. The investigators will refine the peer intervention delivery manual.

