We will also conduct secondary analyses to examine potential moderators of treatment effects. We will specifically examine the baseline factors of injury-related/non-injury-related reason for visit, current intoxication, level of baseline severity of alcohol use/problems, and/or mental health comorbid conditions as potential moderators. In the framework described for Aims 1 and 2 above, we will test an interaction between each factor and group assignment in order to test for moderation. A three-way interaction will be used if strong time*treatment group interactions were observed in prior modeling steps. Because of the number of analyses involved, this will be clearly identified as a secondary analysis in all reporting of the study outcomes. We will measure and analyze dose to inform future implementation in the VHA. First, we will examine baseline factors (e.g., self-efficacy, social support, and readiness to change; psychological distress/psychiatric comorbidity, and alcohol consumption and consequences) that distinguish participants who attend no vs. any peer boosters, and among those who attend at least one session. Other variables (e.g., gender, race, age,

employment, education) will also be included in the models. Second, as an exploratory analysis, we will examine number of sessions attended as a predictor of alcohol use outcomes at later follow-up times within the sub-set of the sample randomized to the peer condition (APM). If this analysis suggests an effect of dosage, we will conduct estimate a complier average causal effect model. In this method, individuals randomized to the BA condition are compared to individuals with similar characteristics in the APM (i.e., who are expected to have attended a similar number of APM sessions had they been randomized to that condition) in order to more accurately test the effect of compliance on outcomes.

Exploratory Aim will result in the collection of structured qualitative interviews to understand barriers and facilitators of implementation of the APM intervention in the ED with a subset of participants, key stakeholders and clinical leaders.

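### The planned complier analysis should not be read as the effect of the booster sessions, because the arms also differ in the ED session

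*Combined protocol and SAP*

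**What the plan says.** The dose analyses are described in the combined protocol and SAP under Data Analysis for Secondary Aim, after the moderator analyses. They run in sequence:

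- First, baseline factors that separate APM participants with no booster from those with at least one.
- Second, as an exploratory step, the number of sessions attended as a predictor of later drinking within APM.
- Third, only if that suggests a dose effect, a CACE model. BA participants are compared with APM participants of similar characteristics, "who are expected to have attended a similar number of APM sessions had they been randomized to that condition". The stated purpose is to test more accurately how compliance affects outcomes.

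The text does not define compliance, name an estimator, or say what is assumed about APM participants who attend no session.

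On the ED session, Peer Mentor Content says "Peer mentors will deliver the brief advice in the ED". Alcohol Brief Advice Content gives both arms scripted, personalised advice and a pamphlet, then adds for one arm: "The APM intervention includes the peer establishing an ongoing relationship with the patient to share their story". Brief Advice Condition says "Participants assigned to BA will receive brief alcohol advice from a research assistant", and Potential Risks agrees. The Human Subjects text on randomisation instead names an ED clinician or the peer mentor as the person giving advice.

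**The concern.** A standard CACE attributes the whole difference between arms to those who comply. It does so by assuming that assignment changes nothing for those who do not comply. Here an APM participant who attends no booster is still due an ED session that differs from BA's in who delivers it and in part of its content. The zero-effect assumption is therefore doubtful, and the plan neither states nor tests it.

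Matching on expected attendance does not remove the difference. A contrast among would-be attenders compares the ED peer session plus boosters with BA's advice. It describes the package in that group and does not separate out the sessions.

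The plan says that dose is analysed to guide later VHA implementation. How much comes from having a peer in the ED, and how much from up to six later contacts, is a question readers will bring to this result.

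**Working it through.** **Inputs**

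- From Power and Sample Size Calculations: 450 randomised and 360 retained, so 180 per arm with equal allocation; "All power analyses used G*Power 3.1.9 software and a two-sided" alpha of .05; "we achieve 80% power to detect an effect size (Cohen's d) of 0.30".
- Assumed: attendance share pi = 0.50, range 0.30 to 0.90. The only related figure is in Preliminary Studies, "only 50% attendance with the therapist-delivered case management", which concerns an earlier intervention and is not a forecast for APM.
- Assumed: delta, the effect of the peer-led ED session over BA's ED advice, from -0.05 to 0.15 SD and equal in attenders and non-attenders. The documents give no value.
- Assumed: an overall arm effect (ITT) of 0.30 SD, the plan's own design effect. Positive values mean benefit.

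**The plan's own figure.** The standard error is sqrt(2/180) = 0.1054. Then 0.30/0.1054 = 2.846, and 2.846 - 1.960 = 0.886, giving power of 81.2% (81.0% with the noncentral t). The stated 80% reproduces. The documents give no figure for the CACE.

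**Algebra.** Let B be the booster effect in attenders, with attendance reduced to yes or no.

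- ITT = delta + pi x B, so B = (ITT - delta)/pi.
- CACE with the non-attender effect set to zero (instrumental-variable, or a mixture model with the same restriction) = ITT/pi = B + delta/pi.
- Matched attender contrast = B + delta. This is the effect of the package in attenders, provided the covariates predict attendance well enough.

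**Numbers** for ITT = 0.30 and pi = 0.50:

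| delta | B | IV CACE | IV error as a booster effect | Matched contrast | Matched error as a booster effect |
|---|---|---|---|---|---|
| -0.05 | 0.70 | 0.60 | -0.10 (-14%) | 0.65 | -0.05 (-7%) |
| 0 | 0.60 | 0.60 | 0 | 0.60 | 0 |
| 0.05 | 0.50 | 0.60 | +0.10 (+20%) | 0.55 | +0.05 (+10%) |
| 0.10 | 0.40 | 0.60 | +0.20 (+50%) | 0.50 | +0.10 (+25%) |
| 0.15 | 0.30 | 0.60 | +0.30 (+100%) | 0.45 | +0.15 (+50%) |

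A simulation with 2,000,000 participants per scenario agrees. At delta = 0.10 it gives 0.600 (IV) and 0.502 (matched).

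**Attendance.** For delta = 0.10, the IV error runs from 0.10/0.30 = +0.33 to 0.10/0.90 = +0.11 SD. It is 50% of B at any pi when ITT is held at 0.30. The matched error stays at 0.10 SD, which is 15% of B at pi = 0.30 and 45% at pi = 0.90.

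**No booster effect.** With B = 0, delta = 0.10 and pi = 0.50, the IV CACE is 0.10/0.50 = 0.20 and the matched contrast is 0.10. The simulation gives 0.202 and 0.102.

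**Relabelling alone does not repair the IV version.** The package effect in attenders is (ITT - (1 - pi) x delta)/pi. At delta = 0.10 this is (0.30 - 0.05)/0.50 = 0.50, not 0.60. The non-attender effect has to be varied as well.

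**Can the non-attender contrast supply delta?** At pi = 0.50 about 90 retained APM participants are non-attenders. With an effective BA size between 180 and 90, the standard error lies between sqrt(1/90 + 1/180) = 0.129 and sqrt(2/90) = 0.149 SD. The 95% interval is about +/-0.25 to +/-0.29 SD, and 80% power is reached only at about 0.36 to 0.42 SD. It cannot resolve effects of 0.05 to 0.15 SD.

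**The case against.** The strongest reply is that the plan never claims to isolate the boosters. It speaks of APM sessions and of compliance, and the trial evaluates APM as a package. The comparison it describes resembles principal-score matching, which is a legitimate estimate of the package effect among would-be attenders under its usual assumptions. On that reading the problem is one of labelling. This stands, and it limits the point. It does not dispose of it: the preceding steps count boosters and sessions, the stated target is compliance, and no estimator is named, so an instrumental-variable version is not excluded.

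A reader might infer that the CACE will overstate the booster effect. The documents do not support that. BA also receives scripted, personalised advice, and the section Guiding Conceptual Framework for Proposed Interventions says that a computerised program secures fidelity in both arms. Delta is therefore only the increment from the peer, and no document shows that it is positive. The sponsor's conceptual model expects peer support to help, which makes a positive delta plausible but is not evidence of its size.

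Two other readings also go too far. The 20%, 50% and 100% errors belong to an estimator that the plan does not name, at invented values of delta. And the ED session is planned for all APM participants but may take place by phone up to two weeks later, so universal receipt is not assured.

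The consequences are bounded. The analysis is a conditional follow-on to an exploratory one. The within-APM dose regression is not affected by a difference between arms. The Dissemination and Implementation Plan ties wider roll-out to the package being effective, not to this CACE.

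**Conclusion.** The point holds as a gap in the estimand. As written, the CACE can be taken for the effect of attending boosters, but the design lets assignment act on people who attend none. The error in that reading is delta/pi for a CACE that fixes the non-attender effect at zero, and delta for a matched attender contrast. It is upward if delta is positive, zero if delta is zero and downward if delta is negative.

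The sizes rest on assumed values of delta, pi and the arm effect, on an ED-session increment that is the same in attenders and non-attenders, and on a yes/no view of a dose that runs from 0 to 6 sessions. They show how sensitive the result is; they do not estimate a bias in this trial. The importance is low: a cheap improvement that changes what an exploratory result can be said to show.

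**What to change.** In the dose paragraph under Data Analysis for Secondary Aim:

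1. Define compliance as attendance at post-ED sessions, and name the CACE estimator.
2. Label the result as the effect of APM (ED peer session plus boosters) among would-be attenders, not as the effect of sessions.
3. Report any instrumental-variable or mixture CACE with the non-attender effect set in turn to, for example, -0.05, 0, 0.05, 0.10 and 0.15 SD.
4. If wanted, report the APM-BA contrast in predicted non-attenders with its confidence interval as a descriptive check. Do not use it as the estimate of the ED-session effect: it is too imprecise and depends too heavily on covariates predicting attendance.
5. Reconcile Brief Advice Condition and Potential Risks with the Human Subjects text on who gives the BA advice, because that determines what delta compares.

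The cost is a few sentences and a five-row table, with no new data. The downside is a wider and possibly less favourable range for the dose result. The Aim 1 comparison and the sample size do not change.
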